8.3.1.1. Reporting SAEs to Pfizer Safety

All SAEs occurring in a participant during the active collection period as described in Section 8.3.1 are reported to Pfizer Safety on the CT SAE Report Form immediately upon awareness and under no circumstance should this exceed 24 hours, as indicated in Appendix 3. The investigator will submit any updated SAE data to the sponsor within 24 hours of it being available.

8.3.1.2. Recording Nonserious AEs and SAEs on the CRF

All nonserious AEs and SAEs occurring in a participant during the active collection period, which begins after obtaining informed consent as described in Section 8.3.1 will be recorded on the AE section of the CRF.

The investigator is to record on the CRF all directly observed and all spontaneously reported AEs and SAEs reported by the participant.

8.3.2. Method of Detecting AEs and SAEs

The method of recording, evaluating, and assessing causality of AEs and SAEs and the procedures for completing and transmitting SAE reports are provided in Appendix 3.

Care will be taken not to introduce bias when detecting AEs and/or SAEs. Open-ended and nonleading verbal questioning of the participant is the preferred method to inquire about AE occurrences.

8.3.3. Follow-up of AEs and SAEs

After the initial AE/SAE report, the investigator is required to proactively follow each participant at subsequent visits/contacts. For each event, the investigator must pursue and obtain adequate information until resolution, stabilization, the event is otherwise explained, or the participant is lost to follow-up (as defined in Section 7.3).

In general, follow-up information will include a description of the event in sufficient detail to allow for a complete medical assessment of the case and independent determination of possible causality. Any information relevant to the event, such as concomitant medications and illnesses, must be provided. In the case of a participant death, a summary of available autopsy findings must be submitted as soon as possible to Pfizer Safety.

Further information on follow-up procedures is given in Appendix 3.

8.3.4. Regulatory Reporting Requirements for SAEs

Prompt notification by the investigator to the sponsor of an SAE is essential so that legal obligations and ethical responsibilities towards the safety of participants and the safety of a study intervention under clinical investigation are met.

The sponsor has a legal responsibility to notify both the local regulatory authority and other regulatory agencies about the safety of a study intervention under clinical investigation. The sponsor will comply with country-specific regulatory requirements relating to safety reporting to the regulatory authority, IRBs/ECs, and investigators.

Investigator safety reports must be prepared for SUSARs according to local regulatory requirements and sponsor policy and forwarded to investigators as necessary.

An investigator who receives SUSARs or other specific safety information (eg, summary or listing of SAEs) from the sponsor will review and then file it along with the SRSD(s) for the study and will notify the IRB/EC, if appropriate according to local requirements.

8.3.5. Exposure During Pregnancy or Breastfeeding, and Occupational Exposure

Exposure to the study intervention under study during pregnancy or breastfeeding and occupational exposure are reportable to Pfizer Safety within 24 hours of investigator awareness.

8.3.5.1. Exposure During Pregnancy

An EDP occurs if:

- A female participant is found to be pregnant while receiving or after discontinuing study intervention.
- A male participant who is receiving or has discontinued study intervention exposes a female partner prior to or around the time of conception.
- A female is found to be pregnant while being exposed or having been exposed to study intervention due to environmental exposure. Below are examples of environmental EDP:
 - A female family member or healthcare provider reports that she is pregnant after having been exposed to the study intervention by ingestion.
 - A male family member or healthcare provider who has been exposed to the study intervention by ingestion then exposes his female partner prior to or around the time of conception.

The investigator must report EDP to Pfizer Safety within 24 hours of the investigator's awareness, irrespective of whether an SAE has occurred. The initial information submitted should include the anticipated date of delivery (see below for information related to termination of pregnancy).

- If EDP occurs in a participant or a participant's partner, the investigator must report this information to Pfizer Safety on the CT SAE Report Form and an EDP Supplemental Form, regardless of whether an SAE has occurred. Details of the pregnancy will be collected after the start of study intervention and until 28 calendar days after the last administration of IP.
- If EDP occurs in the setting of environmental exposure, the investigator must report information to Pfizer Safety using the CT SAE Report Form and EDP Supplemental Form. Since the exposure information does not pertain to the participant enrolled in the study, the information is not recorded on a CRF; however, a copy of the completed CT SAE Report Form is maintained in the investigator site file.

Follow-up is conducted to obtain general information on the pregnancy and its outcome for all EDP reports with an unknown outcome. The investigator will follow the pregnancy until completion (or until pregnancy termination) and notify Pfizer Safety of the outcome as a follow-up to the initial EDP Supplemental Form. In the case of a live birth, the structural integrity of the neonate can be assessed at the time of birth. In the event of a termination, the reason(s) for termination should be specified and, if clinically possible, the structural integrity of the terminated fetus should be assessed by gross visual inspection (unless preprocedure test findings are conclusive for a congenital anomaly and the findings are reported).

Abnormal pregnancy outcomes are considered SAEs. If the outcome of the pregnancy meets the criteria for an SAE (ie, ectopic pregnancy, spontaneous abortion, intrauterine fetal demise, neonatal death, or congenital anomaly), the investigator should follow the procedures for reporting SAEs. Additional information about pregnancy outcomes that are reported to Pfizer Safety as SAEs follows:

- Spontaneous abortion including miscarriage and missed abortion;
- Neonatal deaths that occur within 1 month of birth should be reported, without regard to causality, as SAEs. In addition, infant deaths after 1 month should be reported as SAEs when the investigator assesses the infant death as related or possibly related to exposure to the study intervention.

Additional information regarding the EDP may be requested by the sponsor. Further follow-up of birth outcomes will be handled on a case-by-case basis (eg, follow-up on preterm infants to identify developmental delays). In the case of paternal exposure, the investigator will provide the participant with the Pregnant Partner Release of Information Form to deliver to his partner. The investigator must document in the source documents that the participant was given the Pregnant Partner Release of Information Form to provide to his partner.

8.3.5.2. Exposure During Breastfeeding

An exposure during breastfeeding occurs if:

- A female participant is found to be breastfeeding while receiving or after discontinuing study intervention.
- A female is found to be breastfeeding while being exposed or having been exposed to study intervention (ie, environmental exposure). An example of environmental exposure during breastfeeding is a female family member or healthcare provider who reports that she is breastfeeding after having been exposed to the study intervention by inhalation or skin contact.

The investigator must report exposure during breastfeeding to Pfizer Safety within 24 hours of the investigator's awareness, irrespective of whether an SAE has occurred. The information must be reported using the CT SAE Report Form. When exposure during breastfeeding occurs in the setting of environmental exposure, the exposure information does not pertain to the participant enrolled in the study, so the information is not recorded on a CRF. However, a copy of the completed CT SAE Report Form is maintained in the investigator site file.

An exposure during breastfeeding report is not created when a Pfizer drug specifically approved for use in breastfeeding women (eg, vitamins) is administered in accord with authorized use. However, if the infant experiences an SAE associated with such a drug, the SAE is reported together with the exposure during breastfeeding.

8.3.5.3. Occupational Exposure

An occupational exposure occurs when a person receives unplanned direct contact with the study intervention, which may or may not lead to the occurrence of an AE. Such persons may include healthcare providers, family members, and other roles that are involved in the trial participant's care.

The investigator must report occupational exposure to Pfizer Safety within 24 hours of the investigator's awareness, regardless of whether there is an associated SAE. The information must be reported using the CT SAE Report Form. Since the information does not pertain to a participant enrolled in the study, the information is not recorded on a CRF; however, a copy of the completed CT SAE Report Form is maintained in the investigator site file.

8.3.6. Cardiovascular and Death Events

Not applicable.

8.3.7. Disease Related Events and/or Disease Related Outcomes Not Qualifying as AEs or SAEs

Not applicable.

8.3.8. Adverse Events of Special Interest

Not applicable.

8.3.8.1. Lack of Efficacy

Lack of efficacy is reportable to Pfizer Safety only if associated with an SAE.

8.3.9. Medical Device Deficiencies

Not applicable.

8.3.10. Medication Errors

Medication errors may result from the administration or consumption of the study intervention by the wrong participant, or at the wrong time, or at the wrong dosage strength.

Exposures to the study intervention under study may occur in clinical trial settings, such as medication errors.

| Safety Event | Recorded on the CRF | Reported on the CT SAE Report Form to Pfizer Safety Within 24 Hours of Awareness |
|-------------------|---|--|
| Medication errors | All (regardless of whether associated with an AE) | Only if associated with an SAE |

Medication errors include:

- Medication errors involving participant exposure to the study intervention;
- Potential medication errors or uses outside of what is foreseen in the protocol that do or do not involve the study participant.

Such medication errors occurring to a study participant are to be captured on the medication error page of the CRF, which is a specific version of the AE page.

In the event of a medication dosing error, the sponsor should be notified within 24 hours.

Whether or not the medication error is accompanied by an AE, as determined by the investigator, the medication error is recorded on the medication error page of the CRF and, if applicable, any associated AE(s), serious and nonserious, are recorded on the AE page of the CRF.

Medication errors should be reported to Pfizer Safety within 24 hours on a CT SAE Report Form only when associated with an SAE.

8.4. Treatment of Overdose

For this study, any dose of study intervention greater than tablets for Cohorts 1 and 2, or tablets for Cohort 3, within a 24-hour time period will be considered an overdose.

There is no specific antidote for overdose with PF-06882961. Treatment of overdose should consist of general supportive measures.

In the event of an overdose, the investigator/treating physician should:

1. Contact the medical monitor within 24 hours.

- 2. Closely monitor the participant for any AEs/SAEs and laboratory abnormalities for at least 5 half-lives or 28 calendar days after the overdose of PF-06882961 (whichever is longer).
- 3. Document the quantity of the excess dose as well as the duration of the overdose in the CRF.
- 4. Overdose is reportable to Safety only when associated with an SAE.
- 5. Obtain a blood sample for PK analysis within 2 days from the date of the last dose of study intervention if requested by the medical monitor (determined on a case-by-case basis).

Decisions regarding dose interruptions or modifications will be made by the investigator in consultation with the medical monitor based on the clinical evaluation of the participant.

8.5. Pharmacokinetics

Blood samples of approximately 3 mL each, to provide sufficient *plasma* for PK analysis, will be collected into appropriately labeled tubes containing K₂EDTA, at times defined in the SoA for the applicable cohort (see SoA for Cohorts 1 and 2, and SoA for Cohort 3) and according to the chronology in Appendix 9, with collections occurring prior to dosing with study intervention on the given scheduled visit, and also 1 time within the window of approximately 2 to 6 hours post-dose at specific visits noted in the SoA (ie, also collected post-dose for Cohorts 1 and 2 at V3, V7, V10 and V13, and for Cohort 3 at V3, V7, V11, V15 and V19). The date/time of the blood collections related to PK (both pre- and post-dose samples) should be noted in source documents and captured in the CRF.

Instructions for the collection and handling of biological samples will be provided in the laboratory manual. To maintain sample integrity:

- Any deviations from the PK sample handling procedures (eg, sample collection and
 processing steps, interim storage or shipping conditions), including any actions taken,
 must be documented and reported to the sponsor. On a case-by-case basis, the
 sponsor may make a determination as to whether sample integrity has been
 compromised. Any deviation from the specified sample handling procedure resulting
 in compromised sample integrity will be considered a protocol deviation;
- Any scheduled pre-dose collection (ie, trough concentration) obtained post dose or any post dose samples not collected within the approximately 2-6 hours post dose interval, will be captured as a protocol deviation even if results are deemed evaluable.

As part of understanding the PK of the study intervention, samples may be used for metabolite identification and/or evaluation of the bioanalytical method, as well as for other internal exploratory purposes. These data will not be included in the clinical report.

Samples will be analyzed using a validated analytical method in compliance with Pfizer SOPs.

8.6. Pharmacodynamics

PD parameters evaluated in this study include HbA1c, FPG, FPI, HOMA-IR, and HOMA-B, and will be collected according to the SoA for the applicable cohort (see SoA for Cohorts 1 and 2, and SoA for Cohort 3). The PD parameters will be assessed by the Central Laboratory as part of the clinical laboratory assessments (see Appendix 2).

8.7. Genetics

8.7.1. Specified Genetics

Genetics (specified analyses) are not evaluated in this study.

8.7.2. Banked Biospecimens for Genetics

A 4-mL blood sample optimized for DNA isolation Prep D1 will be collected as local regulations and IRBs/ECs allow.

Banked Biospecimens may be used for research related to the study intervention(s) and adults with obesity. Genes and other analytes (eg, proteins, RNA, nondrug metabolites) may be studied using the banked samples.

See Appendix 5 for information regarding genetic research. Details on processes for collection and shipment of these samples can be found in the laboratory manual.

8.8. Biomarkers

8.8.1. Specified Gene Expression (RNA) Research

Specified gene expression (RNA) research is not included in this study.

8.8.2. Specified Protein Research

Specified protein research is not included in this study.

8.8.3. Specified Metabolomic Research

Specified metabolomic research is not included in this study.

8.8.4. Banked Biospecimens for Biomarkers

Additional Banked Biospecimens in this study are as follows and will be collected at the timepoints outlined in the SoA for the applicable cohort (see SoA for Cohorts 1 and 2, and SoA for Cohort 3):

- 10-mL whole blood (Prep B2 optimized for serum);
- 10-mL whole blood (Prep B1 optimized for plasma).

Banked Biospecimens will be collected as local regulations and IRB/ECs allow.

Banked Biospecimens may be used for research related to the study intervention(s) and adults with obesity. Genes and other analytes (eg, proteins, RNA, nondrug metabolites) may be studied using the banked samples.

See Appendix 5 for information regarding genetic research. Details on processes for collection and shipment of these samples can be found in the laboratory manual.

8.9. Immunogenicity Assessments

Immunogenicity assessments are not included in this study.

8.10. Health Economics

Health economics/medical resource utilization and health economics parameters are not evaluated in this study.

9. STATISTICAL CONSIDERATIONS

Detailed methodology for summary and statistical analyses of the data collected in this study is outlined here and further detailed in a SAP, which will be maintained by the sponsor. The SAP may modify what is outlined in the protocol where appropriate; however, any major modifications of the primary endpoint definitions or their analyses will also be reflected in a protocol amendment. Data from participants enrolled into the original cohort (Cohort 1) and Cohort 2 will be combined for reporting, where data from the placebo and 2-week titration arms will be combined from the 2 cohorts and analyzed together. Data from participants enrolled into Cohort 3 will be analyzed separately unless otherwise specified.

9.1. Estimands and Statistical Hypotheses

Estimands related to percent CFB in body weight:

The primary estimand (Estimand 1) will be the population average treatment effect on the percent CFB in body weight at End of Treatment of PF-06882961 compared to placebo in all evaluable participants while on treatment. For Cohorts 1 and 2, End of Treatment is defined as Week 26. For Cohort 3, End of Treatment is defined as Week 32. This reflects a combination of the 'Hypothetical' and 'While on treatment' strategies as outlined in the ICH-E9 (R1) guidance.³⁵

Measurements after discontinuation of study intervention will be censored and treated as missing data. Missing data due to censoring, study withdrawal or other reasons will have data imputed based on a MAR assumption. The population-based treatment effect will be the mean percent CFB in each PF-06882961 arm compared to placebo. This estimand will similarly be applied to the percent changes from baseline in body weight at all time points through to End of Treatment. For all cohorts, all randomized participants who take at least 1 dose of study intervention will be included.

An additional exploratory estimand (Estimand 7) will be analyzed, which will be the population average treatment effect on the percent CFB in body weight at End of Treatment of PF-06882961 compared to placebo in evaluable participants with no major protocol deviations and while on treatment. This reflects a combination of the 'Hypothetical', 'While on treatment' and 'Principal stratum' strategies as outlined in the ICH-E9 (R1) guidance.³⁵

This is the same as Estimand 1 except that participants with major protocol deviations (eg, inadequate study intervention compliance, use of prohibited medication, etc.) will be excluded from this analysis. Major protocol deviations will be reviewed prior to database lock to identify such participants, with further details included in the SAP.

Estimands related to achieving body weight loss $\geq 5\%$ at End of Treatment:

A secondary estimand (Estimand 2) will be the population odds ratio of the treatment effect of achieving a body weight loss ≥5% from baseline at End of Treatment of PF-06882961 compared to placebo in all evaluable participants while on treatment. This reflects a combination of the 'Hypothetical' and 'While on treatment' strategies as outlined in the ICH-E9 (R1) guidance.³⁵

Measurements after discontinuation of study intervention will be censored and treated as missing data. Missing data due to censoring, study withdrawal, or other reasons (eg, laboratory failure) may be imputed as outlined in the SAP. The population-based treatment effect will be the odds of achieving a body weight loss ≥5% from baseline at End of Treatment on PF-06882961 compared to the odds of achieving this on placebo (ie, odds ratio).

Estimands related to other endpoints:

Estimand 3 is similar to Estimand 1, except the population average treatment effect is on the absolute CFB in waist circumference at End of Treatment. The population based treatment effect will be the mean CFB in each PF-06882961 arm compared to placebo.

Estimands 4, 5 and 6 will utilize the same approach as Estimand 3 for the associated endpoint(s).

Tertiary endpoints may be analyzed using similar estimands or analyzed in a descriptive manner without reference to an estimand. Other supporting estimands may be used for some of the primary and secondary endpoints as a means to examine the robustness of results, compare to available literature and/or be used for future study planning as needed. Details of these estimands and analyses will be presented in the SAP.

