9.3. Analysis Sets

For purposes of analysis, the following analysis sets are defined for the combined Cohorts 1 and 2, and separately for Cohort 3:

| Participant Analysis Set | Description |
|---|---|
| Enrolled | "Enrolled" means a participant's agreement to participate in a clinical study following completion of the informed consent process. Potential participants who are screened for the purpose of determining eligibility for the study, but do not participate in the study, are not considered enrolled, unless otherwise specified by the protocol. |
| Randomly assigned to study intervention | All participants randomly assigned to study intervention regardless of whether or not study intervention was administered. |
| Evaluable | All participants randomly assigned to study intervention and who take at least 1 dose of study intervention. Participants will be analyzed according to the randomized study intervention. |
| Safety | All participants randomly assigned to study intervention and who take at least 1 dose of study intervention. Participants will be analyzed according to the study intervention they actually received. |

| Defined Analysis Set | Description | |
|---|--|--|
| Estimand Set 1 (related to estimands 1, 2, 3, 4, 5 and 6) | All participants randomly assigned to study intervention and who take at least 1 dose of study intervention. For participants who discontinue study intervention, all subsequent values will be censored. | |
| Estimand Set 2 (related to estimand 7) | All participants randomly assigned to study intervention and who take at least 1 dose of study intervention and do not have major protocol deviations. Major protocol deviations will be reviewed prior to database lock to identify such participants, with further details included in the SAP. For participants who discontinue study intervention, all subsequent values will be censored. | |

| PK Concentration Set | All participants randomly assigned to study intervention and who take at least 1 dose of PF-06882961 and in whom at least 1 concentration value is reported. |
|----------------------|--|
|----------------------|--|

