2.2.3. Additional Estimand(s)

An additional exploratory estimand (Estimand 7) will be analyzed, which will be the population average treatment effect on the percent CFB in body weight at End of Treatment of PF-06882961 (danuglipron) compared to placebo in evaluable participants with no major protocol deviations and while on treatment. This reflects a combination of the 'Hypothetical', 'While on treatment' and 'Principal stratum' strategies as outlined in the ICH-E9 (R1) guidance.¹

It includes the following 4 attributes:

- Population: Defined by the inclusion and exclusion criteria to reflect participants with obesity who do not have major protocol deviations
- Variable: Percent change from baseline in body weight at End of Treatment
- Intercurrent events: All data after an intercurrent event of discontinuation of investigational product (IP) will be censored
- Population-level summary: Mean percent change from baseline in each danuglipron arm compared to placebo

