4.1. Identifying Major Protocol Deviations

Major protocol deviations will be identified by review of each protocol deviation on a caseby-case basis to determine whether the associated subject should be excluded from the Estimand Set 2. The list of potential deviations that could be classified as major are: falsely enrolled into study despite violating inclusion/exclusion criteria; non-compliance with study medication; and use of prohibited medications. Other deviations that are identified during the study based on emerging data that are deemed to qualify as major may also be considered. The project statistician will ensure that the list of subjects and the reason for exclusion is clearly documented and provided to programming prior to unblinding and releasing the database.

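### Estimand 7 is partly labelled a principal-stratum estimand, but Estimand Set 2 gives a per-protocol comparison that does not preserve randomisation

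*Protocol*

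**What the plan says.** Estimand 7 is a tertiary/exploratory estimand for percent change in body weight (Protocol 3, SAP 2.2). Protocol 9.1 assigns it to three strategies together: "This reflects a combination of the 'Hypothetical', 'While on treatment' and 'Principal stratum' strategies as outlined in the ICH-E9 (R1) guidance". SAP 2.2.3 repeats this and gives the target as the effect in "evaluable participants with no major protocol deviations and while on treatment".

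The analysis set is Estimand Set 2, defined in Protocol 9.3 as "All participants randomly assigned to study intervention and who take at least 1 dose of study intervention and do not have major protocol deviations". Protocol 9.1 says that Estimand 7 otherwise matches Estimand 1, but "participants with major protocol deviations (eg, inadequate study intervention compliance, use of prohibited medication, etc.) will be excluded from this analysis".

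SAP 4.1 lists three deviations that could be classed as major: "falsely enrolled into study despite violating inclusion/exclusion criteria; non-compliance with study medication; and use of prohibited medications". Others may be added from emerging data. On process it says: "Major protocol deviations will be identified by review of each protocol deviation on a caseby-case basis". The list of excluded participants, with reasons, is to be "provided to programming prior to unblinding and releasing the database".

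SAP 6.1.1.2 then applies the same summaries and MMRM as the main analysis to Set 2, and the efficacy table in SAP Appendix 1 records that participants with major deviations are removed.

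**The concern.** A principal stratum contains the people who would be free of the event whichever of the two treatments they received. Membership is therefore a baseline characteristic, and randomisation still balances the arms within it. Estimand Set 2 is defined by what happened to each person in the arm they were given. For on-treatment non-compliance and for prohibited drugs started after Day 1, that is a post-randomisation outcome which treatment may influence. Those left on danuglipron and those left on placebo need not be the same kind of people.

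At stake is how the Set 2 result is read. The study is meant to inform dose selection, and the full main-analysis output is repeated on this set. A reader who trusts the label could take the result as a causal effect in compliers. In addition, an excluded participant loses every weight, including those measured before the deviation.

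**Working it through.** **1. Label against construction.** The documents state no sample size, power or exclusion rate for Estimand 7, so there is no planned figure to reproduce. The check is whether the plan contains what a principal-stratum analysis needs.

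- *Membership under both arms:* not defined. The population attribute in SAP 2.2.3 refers to participants who do not have major deviations, that is, to observed behaviour.
- *Identifying assumption:* none in either document.
- *Estimator:* the ordinary MMRM on the reduced set (SAP 6.1.1.2).
- *Sensitivity analysis for stratum membership:* none.

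**2. Timing of the deviations.** Eligibility violations precede randomisation. On-treatment compliance is judged from Day 1 through End of Treatment, with an 80% threshold (Protocol 6.4), so it follows randomisation. Prohibited-drug windows open 60 or 90 days before V1 and run to the first follow-up visit (Protocol Appendix 8), so these deviations can fall on either side.

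**3. One scenario.** All inputs are assumed. In each arm 25% are poor adherers who lose 3 points less weight whatever the arm. Exclusions are 20% on danuglipron and 5% on placebo, all from that group. There is no true drug effect.

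- Poor adherers left on danuglipron: (25 − 20)/(100 − 20) = 5/80 = 6.25%.
- Poor adherers left on placebo: (25 − 5)/(100 − 5) = 20/95 = 21.05%.
- Spurious difference: (0.2105 − 0.0625) × 3 = 0.44 points in favour of danuglipron.

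**4. A range from a second model.** Those excluded are the lowest fraction p of a latent adherence score that has correlation ρ with log weight loss. Again there is no true effect.

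Bias = ρ × SD × [λ(p danuglipron) − λ(p placebo)], with λ(p) = φ(z_p)/(1 − p).

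SD = 0.068 on the log scale, the example value in the R code of SAP Appendix 2; the planning SD is blacked out. Arm size is 60 × 0.75 = 45 before exclusions (Protocol 9.2), tested one-sided at 5%. The values of p and ρ are assumptions.

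| Excluded, placebo / danuglipron | ρ | Bias, points for drug | One-sided rejection |
|---|---|---|---|
| 5% / 20% | 0 | 0 | 5.0% |
| 10% / 10% | 0.3 or 0.5 | 0 | 5.0% |
| 5% / 10% | 0.3 | 0.18 | 6.3% |
| 5% / 20% | 0.3 | 0.49 | 9.3% |
| 5% / 20% | 0.5 | 0.82 | 13.3% |
| 5% / 30% | 0.3 | 0.79 | 12.5% |
| 5% / 30% | 0.5 | 1.32 | 20.7% |

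**5. The other direction.** Equal rates do not protect if the reasons differ. Suppose 10% are excluded per arm, weak losers from placebo and strong losers from danuglipron, with ρ of 0.3 and opposite signs. With λ(0.10) = 0.195, bias = 2 × 0.3 × 0.068 × 0.195 = 0.0080, or 0.80 points against the drug. At ρ 0.5 it is 1.33. With 20% excluded per arm it is 1.43 at ρ 0.3 and 2.38 at ρ 0.5.

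**6. Scale.** At 45 per arm and SD 0.068, the difference detectable with 80% power is about 3.5% (2.6% at SD 0.05, 4.1% at SD 0.08).

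**The case against.** The sponsor has fair answers.

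- *Principal stratum is one of three named strategies, and the exclusion rule is stated openly beside it.* True: a careful reader can see a per-protocol set. That does not give the set the property the label claims.
- *Exclusion is not automatic.* Also true. SAP 4.1 lists potential deviations for case-by-case review, and the 80% threshold in Protocol 6.4 triggers re-education, not removal. A reader might infer that every non-compliant participant or prohibited-drug user is dropped; the documents do not say so.
- *The list is fixed before unblinding.* This limits analyst-driven choice. It does not stop selection by arm, because the deviations themselves can depend on the arm.
- *Some deviations precede randomisation.* Conceded. Removing eligibility violations identified without regard to arm need not disturb comparability.
- *The mechanisms are not documented.* Gastrointestinal intolerance causing missed tablets, or lack of effect leading placebo participants to other drugs, is plausible but not stated. Discontinuation of study drug is handled by censoring in both estimand sets, so part of the intolerance pathway acts on Estimands 1 and 7 alike.
- *Censoring does not remove the selection.* It replaces exclusion with a MAR assumption, and cumulative compliance has no natural first-deviation date. Both points stand and limit the fix.

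**Conclusion.** The point holds as one of labelling and interpretation. Set 2 supports a per-protocol comparison; it does not estimate an effect in a principal stratum, and the plan supplies nothing that would let it do so.

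Two stronger readings are tempting and unsupported. The first is that the exclusions bias the result towards danuglipron. The 0.44-point figure is one assumed scenario. In the second model the bias runs from zero to 1.32 points for the drug over the inputs tried, and is 0.80 points against it when equal exclusions have opposite causes, larger if the assumptions are pushed. It vanishes when adherence is unrelated to weight loss, or when rates and reasons match across arms. No exclusion rate or correlation is given in the documents, so neither size nor sign can be settled. The second reading is that the primary result is compromised. It is not affected: Estimand 1 uses Estimand Set 1, which keeps all randomised and dosed participants.

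Because Estimand 7 is exploratory and has no decision rule attached, this is a minor correction, but it changes what may be concluded from the Set 2 output.

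**What to change.** 1. Delete the principal-stratum wording from Protocol 9.1 and SAP 2.2.3. State that the Set 2 analysis is a supplementary per-protocol analysis that does not preserve randomisation. Section 9 of the protocol allows the SAP to modify what it outlines, reserving amendments for major changes to the primary endpoint. The SAP could therefore carry the change, recorded in SAP 2.1, which now lists no modifications.
2. Continue to exclude eligibility violations that predate randomisation.
3. Where a post-randomisation deviation has a recorded date, keep the participant and censor weights from that date, using the same MMRM under MAR as a hypothetical strategy. Prohibited medication qualifies, since Protocol 6.5 already requires start and stop dates for concomitant treatments.
4. Treat non-compliance in the same way only if a dating rule is fixed before unblinding. It could rest on the visit-level compliance in the SAP's Treatment Compliance section (the second section numbered 6.6.1). Otherwise leave it as a labelled per-protocol exclusion.
5. Align the Set 2 definition in Protocol 9.3 and SAP 4, the Estimand 7 objective, and the Estimand Set 2 rows of SAP Appendix 1.

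The relabelling costs only wording. The censoring needs a little more blinded data review and still relies on MAR after censoring. A participant who deviates before the first post-baseline weight (Week 2 in Cohorts 1 and 2, Week 4 in Cohort 3) would still contribute no outcome.
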